Our study hypothesis is that the proportion of children seroconverting after MR vaccine dose at 9 months following administration of an earlier MR vaccine dose at 6 months of age (Arm A) is not different compared with the immunogenicity obtained when MR vaccine dose is administered at 9 months to infants who have had no previous dose of MR vaccine (Arm B). A secondary hypothesis is the incidence and spectrum of adverse reactions following immunization will be similar between doses given at 6 and 9 months (Arm A), and at 9 months.

The following questions are to be answered by the study:

1. What is immunogenicity of MR vaccine at 6 months of age?
2. What is the impact of the 6-month MR dose on immunogenicity of the 9-month MR dose?
3. What are the frequency and severity of adverse reactions following MR vaccination at 6 months and 9 months?
4. What is correlation between the measles and rubella antibody levels in mothers and level of maternal antibodies in infants

Specific Objectives

Primary objectives

1. To assess immunogenicity of MR vaccine at 6 months of age
2. To assess immunogenicity of MR vaccine at 9 months of age among children without prior measles and rubella vaccination, compared with MR vaccine immunogenicity among those who had a prior MR vaccination at 6 months of age

Secondary objectives:

1. To assess the frequency of adverse reactions following administration of MR vaccine at 6 months
2. To compare the immunogenicity of the MR vaccine first dose administered at 6 months vs at 9 months.
3. To assess the proportion of mothers with undetectable, detectable and protective levels of measles and rubella antibodies

4. To determine the extent of variation in measles antibodies in a convenience sample of women of child bearing age in a population with a long standing measles vaccination program
5. To determine the extent of variation in rubella antibodies in a convenience sample of women of child bearing age in a population where rubella vaccine have been recently introduced
6. To determine if variation in antibody levels in infants at 6 months is predominately explained by variation in starting antibody levels in the mother in this population
7. To estimate the half-life of decay of measles and rubella antibodies in infants

Background

Measles

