This study will be an open-label, randomized, 2-arm clinical trial. 620 children will be enrolled and randomized at 6 months of age to one of two study arms. The primary objectives of this study are to assess the immunogenicity of MR vaccine at 6 months, and assess equality of MR vaccine seroconversion administered at 9 months following administration of an earlier MR vaccine dose at 6 months of age compared with MR vaccine dose administered at 9 months only without previous MR vaccination. The study will enrol generally healthy 6 month old infants living in Matlab and who have never received an MR vaccine dose and have no history of measles or rubella. Participants will be followed to 11 months of age.

Infants in this study will be randomly assigned to one of two arms. Infants in Study Arm A will receive MR vaccine at 6 months of age (at enrolment) and at 9 months. Infants in Study arm B will receive MR vaccine only at 9 months.

Blood specimens will be collected from all infants at 6, 9 and 11 months of age. The 6 month sample is a pre-vaccination sample and mainly will be used to determine maternal antibody levels. For arm A, the sample collected at 9 months before the second MR dose will be used to assess antibody levels after the first MR dose at 6 months of age. For study Arm B, the 9 month sample will be used to assess measles and rubella antibody decay rate. The sample collected at 11 months will be used to assess immune response to either a two dose or a one dose schedule (arms A and B, respectively). The study design and participant evaluations are illustrated in the Table.

Table: Schematic representation of study arms

Arm		Age of participant				
		6 months	9 months	11 months	Sample size	Enrollment target (sample size + 10% attrition)
A	MR 6 & 9 months	MR •	MR •	•	279	310
B	MR 9 months	•	MR •	•	279	310
	Total (infants)				558	620
	Mothers	•			558	620

• Indicates blood collection
MR- Measles -rubella vaccination

Blood specimens will be collected from mothers of all enrolled infants at time of enrolment.

Study enrolment and withdrawal

A sample of 620 infants at age 6 months (180 days, +/- 7 days) of age (310 per each study arm) will be enrolled from population living in Matlab area. Inclusion and exclusion criteria are provided below.

Inclusion criteria: Infants

- Healthy infants at 6 months (180 days, +/- 7 days) of age (calendars will be provided to staff)

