Immune response is defined as a 4-fold increase in antibody titers 12 weeks after vaccination (post-6-month visit) compared with 6-month pre-vaccine titers accounting for the expected decline in maternal antibody titers or a change from antibody-negative to positive (i.e. seroconversion). In addition, quantitative data on antibody titers will allow us to assess the magnitude of seroresponse show as $-N$ -fold increases of pre- and post-vaccine titers. Seroprotection is defined as titer of ≥ 120 mIU/mL for measles and rubella >10 IU/mL

Secondary outcomes:

Several secondary outcomes will be assessed:

- 1) Secondary outcome is based on measles titers by MBA (mIU/ml) and rubella titers (IU/mL) by ELISA on sera collected 8 weeks after MR 9-month dose of vaccination (i.e., at 11 months) – post two dose series for participants in Arm A and 1 dose for arm B.
- 2) The safety profile of MR vaccine will be assessed by incidence of specific symptoms/problems. They will be categorized into one of the following three categories:
 - a) Immediate reactions (with emphasis on allergic reactions), occurring in the first 30 minutes post vaccination observed by study staff at the fixed site clinic.
 - b) Adverse events (AE) following 6-month MR dose that may occur during the 48 hours after 6-month MR vaccine administration. AEs will be graded and subcategorized as those deemed related to vaccination or not by the investigator.
 - c) Serious adverse events (SAEs) occurring from vaccination during the course of the study, identified or observed by study staff and/or reported by parent at any time during the study period. SAEs will be subcategorized as those deemed related to vaccination or not by the investigator and reviewed by the local Data and Safety Monitoring Board (DSMB) and icddr,b ERC committee.

Data Analysis

This is an open-label trial clinical trial that compares immunogenicity of MR vaccine schedules. The study will recruit 620 participants in 2 arms. Participants will be enrolled at 6 months of age and followed at 9 months and 11 months of age for a total of 5 months of follow-up.

General analytical issues

The data will be analysed by study investigators that include epidemiologists and statisticians. Statistical packages that would be used for the analysis include R, SAS and STATA.

The immunogenicity of each MR vaccination schedule will be determined by measuring antibody levels:

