- Compare the proportion of participants demonstrating seroconversion at 9 months in both study arms. We will use chi-square test to test for statistical significance
- Compare the change in median titers of measles and rubella antibodies by study arm
- Compare immunogenicity of MR vaccine administered at 6 months (Arm A) vs 9 months (Arm B). Analyse the relationship of infants' immunogenicity to MR vaccine and mothers' level of antibodies
- Analyse the relationship between the levels of infants' maternal measles and rubella antibodies and mothers' antibodies
- Analyse results of adverse events by study arm and compare by age and arm of the study.

Data Safety Monitoring Plan (DSMP)

Records to be kept

Participant data will be collected using case report forms (CRFs). Personal identifiers will not be recorded on any CRFs, biological specimens or electronic records. Participants will be identified by a participant identification number (PID), which will be provided after enrolment and randomization. The PID will be used to link information recorded in CRFs and results from laboratory analysis of biological specimens.

Data entry, cleaning and storage

Records of participants will be kept in a locked cabinet with access restricted to study staff and investigators. All computer records will be kept in a locked room. The computers will be password protected. Only the study staff and investigators will be authorized to access the digital records.

Data from the CRFs will be entered into an electronic database. Checks will be performed to identify and correct data entry errors. After the completion of analysis and publication of study results, the study forms and database will be archived. The forms will be stored in a locked cabinet with access restricted to investigators. The database will be password protected.

Site monitoring plan

Prior to start of the study, Standard Operating Procedures (SOPs) will be developed by investigators in consultation with study staff. Study staff will be trained in study procedures and human subjects' management. After start of the study monitoring of study site will be conducted twice.

During these monitoring visits the following study documents and procedures would be reviewed:

1. Participant records, including consent forms
2. CRFs and other supporting data
3. Adverse event forms
4. Data Safety and Monitoring Board (DSMB) reports
5. Laboratory specimen records
6. Vaccine and biological materials storage and records

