MR vaccine (dose is 0.5ml) per WHO EPI immunization guidelines will be administered following all safety norms. The most common side-effect of MR vaccine injection is pain and redness at the site of administration. The site will be used for monitoring of local reactions.

MR vaccine may have some traces of neomycin. Rarely participants may react to these substances through these reactions. One serious but extremely rare adverse effect to measles vaccine is anaphylaxis. The risk is extremely low - 1 in 3.5 million doses administered(4). Overall, adverse events, with the exception of anaphylactic reactions, are less likely to occur after receipt of a second dose of measles containing vaccine.

It is important to recognize the early symptoms of anaphylaxis and treat such cases immediately. Therefore all infants who receive study vaccine dose will be observed for 30 minutes by medical officer and if any signs of anaphylactic reaction are noticed the medical officer will initiate treatment on the site. Treatment will be free of charge. This child will not receive future MR vaccine doses. Special notes will be made in his medical card. Although we do not expect any additional side effects the 6 months infants will be followed for 48 hours after receipt of the first MR study dose because they receive MR vaccination before the age of routine vaccination in Bangladesh. Most common adverse events in infants at 6 months after administration of measles containing vaccine are fever, mild rash, redness and swelling of injection site. Most adverse effects are mild and self-limited.

Forty eight hours after vaccine administration at 6 month a study staff will visit respondents at their home to monitor and document any adverse effects following immunization.

All costs will be provided by the study for infants who experience severe adverse events in this study.

Participant Privacy

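### The 6- versus 9-month safety comparison names no contrast; if second doses enter it, or follow-up is unequal, the 6-month dose looks worse with no age effect

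*Combined protocol and SAP*

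**What the plan says.** All references are to the combined protocol and SAP.

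- **Design (Study design).** "Infants in Study Arm A will receive MR vaccine at 6 months of age (at enrolment) and at 9 months". Arm B has a single dose, given at the 9-month visit. So the Arm A 9-month dose is always a second dose, and the Arm B 9-month dose is always a first.
- **Safety objective (Specific Objectives).** "To assess the frequency of adverse reactions following administration of MR vaccine at 6 months".
- **Safety hypothesis (Hypothesis to be tested).** The incidence and spectrum of reactions "will be similar between doses given at 6 and 9 months (Arm A), and at 9 months". By context, the last term is Arm B's dose.
- **Safety analysis (Data Analysis, closing list of planned comparisons).** "Analyse results of adverse events by study arm and compare by age and arm of the study". No contrast, denominator or test is named for adverse events.
- **Expected effect of dose number (Potential risks to participants).** "adverse events, with the exception of anaphylactic reactions, are less likely to occur after receipt of a second dose of measles containing vaccine".
- **Ascertainment.** The outcome category is "Adverse events (AE) following 6-month MR dose that may occur during the 48 hours after 6-month MR vaccine administration", captured at a home visit two days after that dose. The section on the 9-month site visit rules out a home visit after the 9-month dose in either arm. Common to both ages are 30 minutes of observation and a question to parents, at each visit, about events since the previous one. The adverse event form records time of onset (Recording, monitoring and reporting of adverse events).

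**The concern.** The practical safety question is whether a dose at 6 months causes more reactions than the routine dose at 9 months. Within Arm A, moving from 6 to 9 months changes two things at once: the infant's age, and whether the dose is the first or the second. By the protocol's own statement the second change lowers the reaction rate. Equal rates at Arm A's two doses are therefore not what the absence of an age effect predicts, although the hypothesis sets those two doses side by side and expects them to be similar. A comparison by age that pools the 9-month doses of both arms has the same fault in diluted form, because about half of the pooled doses are second doses.

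Unequal follow-up works in the same direction. Reactions after the 6-month dose have an extra active source and a longer reporting interval, so more of them will be recorded. Both mechanisms could lead a reader to conclude that the early dose is less well tolerated when it is not.

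**Working it through.** The documents give no reaction rate by age, no second-dose reduction, and no power or sample size for safety. There is no stated figure to reproduce, and the size of the bias cannot be derived from them. What follows shows its form and an illustrative range.

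**Inputs**
- p, the first-dose reaction rate at 9 months: assumed 5% to 15%. The scale is borrowed from the Safety monitoring section, which puts fever of at least 39.4 °C at about 5% to 15%, on days 7 to 12. It is a scale only.
- s, the second-dose rate as a fraction of p: assumed 0.25 to 0.75. The documents support only s < 1.
- a, the true ratio of the 6-month first-dose rate to the 9-month first-dose rate. No age effect means a = 1.
- Equal numbers of 9-month doses in the two arms, from the 1:1 allocation.
- Equal ascertainment, for the moment.

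**Expected differences, 6 months minus 9 months**
- First dose against first dose (Arm A at 6 months, Arm B at 9 months): ap − p. This is the true age effect, and it is 0 when a = 1.
- Within Arm A: ap − sp = (ap − p) + p(1 − s). The bias is +p(1 − s).
- Arm A at 6 months against pooled 9-month doses: ap − (p + sp)/2 = (ap − p) + p(1 − s)/2. The bias is +p(1 − s)/2.

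When s < 1 both biases are positive whatever the value of a.

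**Spurious 6-month excess with no age effect, in percentage points**

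| p | s | Within Arm A | Against pooled 9-month doses |
|---|---|---|---|
| 5% | 0.75 | 1.25 | 0.625 |
| 5% | 0.50 | 2.5 | 1.25 |
| 5% | 0.25 | 3.75 | 1.875 |
| 10% | 0.75 | 2.5 | 1.25 |
| 10% | 0.50 | 5.0 | 2.5 |
| 10% | 0.25 | 7.5 | 3.75 |
| 15% | 0.75 | 3.75 | 1.875 |
| 15% | 0.50 | 7.5 | 3.75 |
| 15% | 0.25 | 11.25 | 5.625 |

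Central illustration: p = 10% and s = 0.5 give 10% − 5% = 5 points within Arm A. Against pooled doses they give 10% − (10% + 5%)/2 = 10% − 7.5% = 2.5 points.

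**Ascertainment**

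| | 6-month dose, Arm A | 9-month dose, either arm |
|---|---|---|
| 30-minute observation | yes | yes |
| Home visit at 48 hours | yes | no |
| Recall interval to next site visit | about 9 − 6 = 3 months | about 11 − 9 = 2 months |

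The second and third rows add recorded events to the 6-month dose only. This also affects the first-dose against first-dose contrast, which is free of dose number but not of unequal follow-up. The same Safety monitoring section places rash from days 7 to 10, so both it and the fever above fall outside the 48-hour window. For these reactions the only source is what parents report at a later visit.

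**The case against.** **The plan may already contain the right comparison.** Age crossed with arm gives three cells: Arm A at 6 months, Arm A at 9 months and Arm B at 9 months. Each cell has one dose number, and the clean contrast is among them. No section says that 9-month doses will be pooled. This stands. It means that the fault is an unnamed contrast, not a confounded design. It does not dispose of the point, because the hypothesis does set Arm A's two doses against each other and the analysis wording admits the biased readings as easily as the clean one.

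**The consequence is limited.** The objective is to describe frequency after the 6-month dose, and that frequency is untouched. The hypothesis is secondary, with no margin or power. The chi-square test is named for immunogenicity proportions and not for adverse events. This also stands: the harm is to interpretation.

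**Unequal follow-up is the more direct threat.** Agreed, so the remedy has to deal with both.

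**Comparing schedules is a legitimate question.** A two-dose against one-dose comparison by arm has programme value. It can stay, provided that it is not read as an age effect.

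**A stronger reading is tempting:** that the plan could also hide a real 6-month excess. The documents do not support it. In any 6- versus 9-month contrast a lower second-dose rate only adds to the apparent excess. It can create one, or mask a lower 6-month rate, but it cannot conceal an excess. Concealment would need Arm A's two doses to be averaged per dose and set against Arm B. With p = 10%, a = 1.5 and s = 0.5, that gives (15% + 5%)/2 = 10% against 10%. No section proposes such an average, and the 48-hour outcome category covers the 6-month dose alone.

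**Conclusion.** The point holds as a gap in specification of the secondary safety comparison. Any 6- versus 9-month comparison that puts second doses on the 9-month side is biased towards a worse-looking 6-month dose, and unequal follow-up adds to that bias. The direction rests on the protocol's own statement about second doses and on its visit schedule.

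The size is not known. Across the assumed ranges the dose-number bias is 1.25 to 11.25 percentage points within Arm A and about 0.6 to 5.6 points against pooled doses, with 5 and 2.5 points in the central illustration. The bias from follow-up cannot be quantified from the documents.

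A reader might go on to infer a probability of a false safety signal. That is not supportable: no test is specified for adverse events, the reaction rates are assumed, and the fever rate used for scale belongs to days that the home visit does not cover. Nor is age inseparable from dose number in this trial, because Arm B supplies a randomised first dose at 9 months.

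**What to change.** In the hypothesis section and in the adverse event item of the planned comparisons, name two contrasts:

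1. **Age contrast:** Arm A first dose at 6 months against Arm B first dose at 9 months. Tie the expectation of similar reactions to this contrast.
2. **Prior-dose contrast at the same age:** Arm A second dose against Arm B first dose, both at 9 months.

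Report each as a per-infant risk difference with a 95% confidence interval, and do not pool first and second doses.

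For contrast 1, use only events collected alike: the 30-minute observation, and events reported at the next site visit whose recorded onset falls within the same fixed window after the dose. State that window before the adverse event data are analysed. Report home-visit findings descriptively, for the 6-month dose only. A per-infant comparison of the two-dose with the one-dose schedule may remain if it is labelled as such.

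**Cost.** The change is to wording and uses data already planned, with no extra visits or samples. The note on the assay change implies that field data collection is complete, so the analysis is the part that can still be settled. The price is fewer events in the comparison. Delayed reactions would rest on parental recall, at a lag of about three months for the 6-month dose and two for the 9-month dose; a fixed window equalises the period counted but not that lag. Background illness at the two ages also stays in contrast 1 and should be listed as a limitation.
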